9 STUDY PLAN

9.1 Study Time and Events Schedule

Study assessments and corresponding event schedules are summarized in the schedule of assessments (Table 9-1).

9.1.1 Screening Phase

Screening assessments will be performed up to 42 days prior to Day 1 of the double-blind treatment period. All screening evaluations must be completed and reviewed to confirm that potential subjects meet all eligibility criteria.

9.1.2 Rescreening

If a subject has not met all eligibility criteria at the end of the Screening period, the subject will be registered as a screen fail. Screen fail subjects may be eligible for rescreening 1-time following consultation with the Sponsor and Medical Monitor.

Rescreened subjects must first be registered as screen failures and subsequently registered as rescreens. Once the subject is registered as rescreened, a new screening window will begin. The rescreened subject will be reassigned a new unique Subject Identifier and the previous Subject Identifier will be noted. If the rescreening period begins more than 30 days after the original signing of the Informed Consent Form (ICF), all screening procedures, including ICF, must be repeated.

If the subject does not meet eligibility criteria for laboratory tests, the subject may undergo repeat laboratory tests up to 2 additional times during the 6-week Screening period. Repeat of laboratory tests is not considered rescreening.

Table 9-1 Schedule of Assessments

Study Period	Screening	Double-blind Treatment						Double-blind Extension			Follow-up
		Visit 1 (Randomization)	Visit 2 3 ^g	Visit 4 5 ^g	Visit 6 7 ^g (EOT/Rand)	Visit 8 ^g	Visit 9 ^g	Visit 10 (EOT/DBE)			
Study Week	Week -6 to Week 0	Week 2	Week 4	Week 8	Week 12	Week 26	Week 28	Week 32	Week 39	Week 52	Visit 12 ^g (EOS)
Study Day ± Window	Day -42 to Study Day ¹	Day 1	Day 15±5	Day 29±7	Day 57±7	Day 85±7	Day 183±7	Day 197±7	Day 225±7	Day 274±7	Day 365±7
Informed consent/assent ^b	X										
Inclusion/exclusion criteria evaluation	X	X									
Demographics	X										
Medical history	X	X									
Randomization	X	X									
Body weight	X	X	X	X	X	X	X	X	X	X	
Height	X										
Physical examination ^c	X	X	X	X	X	X	X	X	X	X	
Vital signs ^d	X	X	X	X	X	X	X	X	X	X	
12-lead ECG ^e	X										
Hematology/ coagulation, biochemistry & urinalysis ^g	X	X	X ^g	X	X ^g	X	X ^g	X ^g	X	X	X
Blood collection for porphyrin and protoporphyrin levels ^h	X		X		X	X			X	X	

Study Period	Screening	Double-blind Treatment						Double-blind Extension			Follow-up
Visit Number	Visit 1	Visit 2 (Randomization)	Visit 3 ^g	Visit 4	Visit 5 ^g	Visit 6	Visit 7 ^p (EOT/ Rand)	Visit 8 ^g	Visit 9 ^g	Visit 10	Visit 11 ^q (EOT/ DBE)
Study Week	Week -6 to Week 0	Week 2	Week 4	Week 8	Week 12	Week 26	Week 28	Week 32	Week 39	Week 52	Week 32 or 58
Study Day ± Window	Day -42 to Study Day ^a	Day 1	Day 15±5	Day 29±7	Day 57±7	Day 85±7	Day 183±7	Day 197±7	Day 225±7	Day 274±7	Day 365±7
Fitzpatrick skin type assessment ^s	X		X		X		X	X		X	X
Pregnancy test ^t	X	X	X		X		X	X		X	X
PK sampling (blood) ^y		X		X		X	X		X	X	
Blood sampling for PGx ^b		X									
Dispensing of study medication	X	X	X		X		X	X		X	
Medication accountability		X		X		X		X		X	
Subject Question for study medication ^k						X					
PROMIS-57		X				X	X		X	X	X
PGIC				X			X			X	
PGIS		X	X		X		X		X	X	X
EOT/Exit interview questionnaire ^l						X					
Sunlight exposure diaries ^m											
In-clinic sunlight exposure test ⁿ	X									X	

Study Period	Screening		Double-blind Treatment					Double-blind Extension			Follow-up	
	Visit Number	Visit 1	Visit 2 (Randomization)	Visit 3 ^g	Visit 4	Visit 5 ^g	Visit 6	Visit 7 ^h (EOT/ Rand)	Visit 8 ^g	Visit 9 ^g	Visit 10	
Study Week	Week -6 to Week 0		Week 2	Week 4	Week 8	Week 12	Week 26	Week 28	Week 32	Week 39	Week 52	Week 32 or 58
Study Day ± Window	Day -42 to Study Day ^a	Day 1	Day 15±5	Day 29±7	Day 57±7	Day 85±7	Day 183±7	Day 197±7	Day 225±7	Day 274±7	Day 365±7	Day 407±7
Melanin density evaluation		X		X		X	X				X	X
Nevi evaluation ^o		X		X		X	X				X	X
Concomitant medication												
Adverse events												

Abbreviations: DBE = double-blinded extension; ECG = electrocardiogram; EOS = end of study; EOT = end of treatment; PGIS = Patient Global Impression of Change; PGIS = Patient Global Impression of Severity; PGx = pharmacogenomic(s); PK = pharmacokinetic; PROMIS = Patient-Reported Outcomes Measurement Information System.

^a A minimum of 7 days of outside exposure data is required in the 14 days prior to randomization.

^b Blood samples will be collected for PGx analysis for those subjects who have specifically given informed consent/assent for optional PGx analysis at Visit 2.

^c Complete physical examination will be performed at Visit 1 and an abbreviated physical examination will be performed at all other specified time points.

^d Vital signs include measurement of sitting blood pressure, respiratory rate, pulse rate, and body temperature.

^e ECG will be assessed at Visit 7 for subjects who do not elect DBE. For subjects that received MT-7117 during the blinded period will continue the DBE in the same treatment arm and remain blinded. Subjects that received placebo will be randomized to receive MT-7117 [REDACTED] or [REDACTED] in 1:1 ratio for the 26 weeks DBE period. For subjects with the [REDACTED] dose will be administered without re-randomization.

^g At Visits 3, 5, 8, and 9, subjects may have mobile units or in-clinic visits to measure liver function markers (ALT, AST, GGT, ALP, direct and total bilirubin). Blood samples for liver function markers will be shipped to the central laboratory.

^h Plasma total porphyrins and erythrocyte protoporphyrin will be assessed at Visits 1, 4, 6, 7, 10, and 11.

ⁱ For female subjects of child-bearing potential, a serum pregnancy test will be performed at Visit 1 and a urine pregnancy test will be performed at Visits 2, 4, 6, 7, 10, 11, and 12.

^j For subjects who are ≥18 to ≤75: PK blood samples for MT-7117 will be collected and processed at Visit 2 (pre-dose), Visits 4, 6, 10, and 11 (any time), and Visit 7 (at the visit and 3 to 4 hours after the first PK sample collection [both post-dose]). Date and time of most recent dose, and date and time of PK sample collection will be recorded. Subjects who are ≥12 to ≤17 years old will have 9 PK samples at 3 time points collected: Visit 2 at 2, 4, 6, and 8 hours post-dose, Visit 6 at pre-dose and 3 hours post-dose, and Visit 7 at pre-dose and 2, and 4 hours post-dose.

^k Subjects will be asked whether they believe they received active or placebo treatment.

- ¹ EOT/Exit interview will only be performed in selected countries.
- ^m Sunlight exposure data, presence of prodromal symptoms and sunlight-induced phototoxic reactions, their severity, and their onset/duration will be collected from Visits 1 through 12.
- ⁿ Diary training will be performed at the first in-clinic visit during the screening period.
- ⁿ In-clinic sunlight exposure test should be done once before randomization (Visit 1 or 2) and once at Visit 7. For subjects who elect DBE, the test is also performed at Visit 11.
- ^o Nevi evaluation will be performed locally by a dermatologist or qualified site staff. Baseline nevi evaluation will be performed at any time during the Screening period before Randomization (Visit 1 or 2). The Nevi evaluation at Visit 12 is to assess for the reversibility if any suspicious nevi changes were observed during treatment as per the Investigator's (and/or dermatologist's or other qualified site staff) judgment. Any follow-up will be recorded in the eCRF. Nevi assessment will be described in a separate document.
- ^p These assessments will be performed at Week 26 or early termination visit from the double-blind treatment period. If the visit is due to early termination, no double-blinded extension study medication is to be dispensed.
- ^q These assessments will be performed at Week 52 or early termination visit from the double-blinded extension period.
- ^r All subjects will return to the study site for a 6-week follow-up visit at Week 38 (Week 32 if DBE is not elected) or 6 weeks after early termination visit. For discontinued subjects who will not revisit the clinic, the site will perform scheduled phone calls for the collection and source documentation for safety information (AEs, concomitant medication, and date of last dose of medication).
- ^s Fitzpatrick skin type assessment should be done once before randomization.

9.2 Subject Informed Consent

Before performing any study procedures, the Investigator (or designated personnel) will ensure that the subject is given full and adequate oral and written information about the study and the subject must sign the Informed Consent Form (ICF), as described in Sections 10.1 and 15.2.1.

9.3 Post-Study Access to Treatment

MT-7117 will not be available to subjects following completion or termination of the study, in accordance with the study information given to the subjects.

9.4 Unscheduled Visits

An unscheduled visit is defined as follows:

- Any visit to the Investigator site outside of the protocol specified time points due to safety reasons or when a repeated measurement is required (e.g., obvious measurement errors, measuring device failure, confirmation of out-of-range results), where the subject is seen by study personnel.
- Any visit by the mobile units or in-clinic visits outside of the protocol specified time points when a repeated measurement of liver function markers is required (e.g., safety reasons, obvious measurement errors, measuring device failure, confirmation of out-of-range results).

Additional unscheduled samples for safety assessments may be performed at the discretion of the Investigator, if deemed necessary. All unscheduled visits and assessments performed during the visits will be recorded in the eCRF.

10 STUDY PROCEDURES

Procedures will be performed according to the schedule of assessments (Table 9-1).

10.1 Informed Consent Form

The Investigator or designee will fully explain the nature of the study to subjects using the Institutional Review Board (IRB)/Independent Ethics Committee (IEC) approved ICF. When the subject agrees to participate in the study, the subject must voluntarily sign an ICF before the initiation of any study procedures. A copy of the signed and dated informed consent (or assent for adolescent subjects) document will be given to the subject. The signed and dated original ICF will be retained by the Investigator. Informed consent will be obtained from all subjects. An assent will be obtained from all adolescent subjects. A subject cannot enter the study until he or she has signed and dated the ICF.

For adolescent subjects, according to local regulations, one or both parents or a legally acceptable representative must be informed of the study procedures and must sign the applicable informed consent form approved for the study prior to clinical study participation. In such cases, records on the relationship between the subject and the parent(s)/legal representative consenter should be maintained in source documents. The explicit wish of an adolescent who is capable of forming an opinion and assessing this information to refuse participation in, or to be withdrawn from, the clinical study at any time should be considered by the investigation.

The Investigator or designee is responsible for ensuring that the subject understands the risks and benefits of participating in the study, including answering any questions the subject may have throughout the study and sharing any new information in a timely manner that may be relevant to the subject's willingness to continue his/her participation in the study.

Any information conveyed to the subject in advance of screening visit 1 used to recruit subject or enable travel arrangements require IRB/IEC submission and approval per local requirement.

Certain procedures outlined in this protocol are optional and are not required if subject opts out. These procedures include sample collection for Pharmacogenomics (PGx) testing obtained for the noted exploratory endpoints. Biopsy may be requested for safety if they arise via the post-baseline nevi assessments per the investigator judgement. For PGx testing, DNA and messenger ribonucleic acid (mRNA) will be measured. These procedures will be performed only on subjects who specifically provided consent/assent to undergo these optional procedures. Separate informed consent/assent for PGx testing will be required.

10.2 Demographics

The following subject characteristics will be recorded at Screening: year of birth, sex, weight, height, ethnicity, race, and a unique subject identifier in MT-7117-A01 study only if the subject took placebo in the MT-7117-A01 study.

10.3 Medical History

Medical, medication, smoking, alcohol, psychiatric disease, and surgical history will be recorded. Medical/surgical history includes any medical condition or surgical history before Screening. In addition, the detailed history of hepatic injury (e.g., viral hepatitis, autoimmune hepatitis, nonalcoholic steatohepatitis, hypoxic/ischemic hepatopathy, biliary tract disease) will be recorded.

10.4 Prior and Concomitant Medication

Prior medications are defined as any medication taken before Screening.

Any prior medication, including prescription and over-the-counter medications, taken within 1 month before Screening will be recorded on the eCRF. Information recorded will include: name of medication, dose, duration of and reason for use. It should be noted if subjects have ever used afamelanotide.

Concomitant medication is defined as any medication, other than study medication, which is taken during the study, including prescription, over-the-counter medications, herbals, dietary supplements, and recreational drugs. All concomitant medications taken while the subject is participating in the study will be recorded.

Concomitant medication will be given only if deemed necessary by the Investigator or the subject's personal physician.

10.5 Fitzpatrick Skin Type Assessment

A Fitzpatrick scale test¹⁰ will be completed at the times shown in the schedule of assessments (Table 9-1). The results will be recorded in the source documents and the eCRF. The score for defining skin type will be recorded in the source documents. An example of the Fitzpatrick scale test is presented in Section 18.3 (Appendix 3).

10.6 Subject Questionnaire for Study Medication

At Week 26 or early termination visit (Visit 7), subjects will be asked whether they believe they received active or placebo treatment. The results will be recorded in the source documents and the eCRF.

10.7 Efficacy Assessments

10.7.1 Primary Efficacy Endpoint

10.7.1.1 Sunlight Exposure Diary – Outdoor Exposure and Prodromal Symptoms

Subjects will complete the sunlight exposure diary on a daily basis from Screening to the follow-up visit. The sunlight exposure diary is a smartphone device and examples of the questions (extract) are presented in Section 18.4 (Appendix 4).

Subjects will record their sunlight exposure time in the sunlight exposure diary. For each sunlight exposure, they will record the presence, duration (onset time of the first symptom and recovery time), and severity of the prodromal symptoms (see below). The severity of prodromal symptoms will be measured using an 11-point Likert scale ranging from 0 to 10, with 0 indicating no pain or discomfort and 10 indicating greatest severity of pain.

Prodromal symptom is the terminology used for the warning signals that have been described by EPP and XLP patients through patient roundtable discussions and literature as their signal to get out of the sun. Subjects will be instructed to recognize the following photo-induced symptoms as prodromal:

- Burning/hotness/heating up
- Tingling
- Itching/scratchy
- Stinging
- Others

Subject responses in the sunlight exposure diary will be used to investigate the primary efficacy endpoint. The data from the diary will also be used for the secondary and other efficacy assessments.

Further details will be provided in a separate study reference manual, and statistical assessment methods for this study endpoint are described in Section 14.3.2.1.

10.7.2 Secondary and Other Endpoints

10.7.2.1 Sunlight Exposure Diary – Phototoxic Reactions

A phototoxic reaction is characterized based on patient input as a painful skin reaction that occur subsequent to a prodromal symptom. Depending on duration protracted sun exposure beyond occurrence of a prodrome, the intensity of the skin reaction can be moderate to severe and lasting up to several days.

Sunlight-induced phototoxic reactions, its severity, and duration (onset time and recovery time) will also be recorded separately in the dedicated part of the sunlight exposure diary.

The severity of sunlight-induced phototoxic reactions will be measured using an 11-point Likert scale ranging from 0 to 10, with 0 indicating no pain and 10 indicating greatest severity of pain.

10.7.2.2 In-Clinic Sunlight Exposure Test

In-clinic sunlight exposure test will be performed at the times shown in the schedule of assessments (Table 9-1).

Site staff will lead subjects into a setting with sun-light exposure and subjects will be provided with a timer (e.g. preferably outdoors) to collect the period of time it takes for the subject to experience the onset of the first prodromal symptom. Upon entry of the subject into the sunlight

exposed setting, the timer will be started (as well as the time of day). Site staff will direct the subject to stop the timer upon the onset of the first sensation of prodromal symptoms. The time in minutes obtained from the time of sun-light exposure to onset of prodromal symptoms, as well as the time of day the assessment was performed, will be collected. This assessment should be performed in a manner that lends consistency to the amount of daylight exposure and/or intensity where feasible. Where weather conditions restrict the ability to capture this assessment, it will be so noted on the source and eCRF. Further instructions will be outlined in the protocol procedures manual.

10.7.2.3 Melanin Density Evaluation

Sites will assign unblinded personnel who will receive melanin density measurement training. Melanin density will be assessed at the times shown in the schedule of assessments (Table 9-1) using a hand-held spectrophotometer. The effect on pigmentation will be assessed in all subjects by measuring melanin density on 6 skin segments (forehead, left cheek, right inside upper arm, left medial forearm, right-hand side of abdomen, and left-hand side of buttock) as measured by spectrophotometer. The site will be required to successfully collect the data with specialized software and transfer to the designated data management entity.

Further details about the evaluations and unblinding protection will be provided in a separate study reference manual.

10.7.2.4 Patient-Reported Outcomes Measurement Information System Questionnaire

The PROMIS-57 questionnaire will be completed at the times shown in the schedule of assessments (Table 9-1).

The PROMIS-57 assesses each of 7 domains with 8 questions per domain; physical function, anxiety, depression, fatigue, sleep disturbance, ability to participate in social roles and activities, and pain interference (including pain intensity). The effect of treatment with MT-7117 on QOL in subjects with EPP or XLP will be assessed by measuring the change in PROMIS-57 score (total and each domain).

An example of the PROMIS-57 questionnaire is presented in Section 18.5 (Appendix 5).

10.7.2.5 Patient Global Impression of Change

The PGIC is used to assess the subject's rating of overall improvement. Subjects rate their perceived change on a 7-point scale from 'very much improved' to 'very much worse'. The PGIC will be used to evaluate the subjects' perspective on the meaningfulness and impact of an increased time to prodromal symptoms and their quality of life.

The PGIC will be completed at the times shown in the schedule of assessments (Table 9-1). An example of the PGIC is presented in Section 18.6 (Appendix 6).

10.7.2.6 Patient Global Impression of Severity

The PGIS is used to assess the subject's rating of severity of overall status. Subjects rate their perceived change on a 5-point scale from 'none' to "very severe".

The PGIS will be completed at the times shown in the schedule of assessments (Table 9-1). An example of the PGIS is presented in Section 18.7 (Appendix 7).

10.7.2.7 Qualitative End of Treatment/Exit Interview Questionnaire

The objective of the qualitative interviews is to elicit the key symptoms and impact associated with EPP or XLP as well as the effect of MT-7117 in relation to symptoms and impact experienced during the clinical study as described by patients in their own words.

A qualitative interview will be conducted by phone and within 14 days after completion of the end of treatment/early termination visit (see Table 9-1). A single individual telephone interview will be conducted with English-speaking subjects who provide informed consent/assent to participate in the interview. These interviews will be performed at selected sites/countries.

10.8 Pharmacokinetic Assessments

Blood samples will be collected by direct venipuncture in a suitable forearm vein. The actual date and time of each blood sample and the most recent dose date and time will be recorded in the source document and eCRF.

For each PK assessment in ≥ 18 to ≤ 75 years old, 1 blood sample of approximately 4 mL will be collected to ensure there is sufficient plasma for primary and contingency samples.

For each PK assessment in ≥ 12 to ≤ 17 years old, 1 blood sample of approximately 2 mL will be collected.

Subjects enrolled in Japan will have PK samples collected as described in a separate document.

Sample handling details will be described fully in a separate document.

10.9 Safety Assessments

Please refer to Section 12 for details of AE management.

10.9.1 Physical Examination

The complete physical examination will consist of a routine assessment of major body systems: abdominal, respiratory, cardiovascular, general appearance, head, eyes, ears/nose/throat, lymph nodes, musculoskeletal, neck, neurological, dermatological, and 'other'.

The abbreviated physical examination will consist of a routine assessment of the following body systems: abdominal, respiratory, cardiovascular, general appearance, and 'other'.

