The number of subjects with post-baseline assessments $\geq 2 \times$ ULN and $\geq 3 \times$ ULN and so on will be calculated for ALT, AST, GGT, ALP, direct and total bilirubin and summarized by treatment group for each post-baseline visit.

The figure of mean (or median) and standard error value of ALT, AST, total bilirubin and alkaline phosphatase by visit will be plotted.

Vital signs and electrocardiogram data

Vital signs and 12-lead ECG variables and changes from baseline will be descriptively summarized at each visit by treatment group.

The baseline for the vital sign parameters and 12-lead ECG measurements will be the last valid assessment obtained on Day 1 prior to the administration of double-blind treatment period.

For ECGs, number and percentage of subjects meeting the criteria listed below will be presented in tables:

- Baseline Corrected QT interval (QTc) <450 msec and >500 msec at EOT
- Baseline QTc <450 msec and 500 msec \geq QTc > 480 msec at EOT
- Baseline QTc <450 msec and 480 msec \geq QTc > 450 msec at EOT
- Increase from baseline at EOT in QTc > 30 msec
- Increase from baseline at EOT in QTc > 60 msec

These criteria will be applied to both Corrected QT interval using Bazett's formula (QTcB) and Corrected QT interval using Fridericia's formula (QTcF).

Physical examination and Nevi evaluation

Physical examination data will be summarized descriptively (number and percentage of the subjects) in tables by treatment and time point.

Nevi appearance will be summarized descriptively (number and percentage of the subjects) in tables by treatment and analysis visit for subjects' suspicious nevi found.

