6 STATISTICAL CONSIDERATIONS

6.1 Descriptive Statistics

Continuous data will be summarized descriptively using the number in the analysis set (N), the number of observations (n), mean, standard deviation (SD), median, minimum and maximum. Categorical data will be summarized using frequency counts and percentages. The denominator for the percentages will be the total number of subjects in the treatment group and analysis population being presented, unless otherwise specified (e.g. on some occasions, percentages may be calculated out of the total number of subjects with available data at a particular visit and/or time point).

Unless otherwise specified, all data will be summarized by analysis visits and treatment group.

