8.3.5 Physical Examinations

Physical examination will be summarized with the number and percentage of the subjects for clinically relevant categories (Normal, Abnormal(Not Clinically Significant, Clinically Significant)).

- Abdominal
- Cardiovascular
- General Appearance
- Head
- Eyes
- Ears/nose/throat

- Lymph nodes
- Musculoskeletal
- Neck
- Neurological
- Dermatological
- Other

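### SAP 8.3.5 omits the respiratory system from the physical-examination summary and does not say at which visits, or over which subjects, each body system is tabulated (minor)

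*Protocol*

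**What the plan says.** Protocol 10.9.1 defines two examinations. For the complete one: "The complete physical examination will consist of a routine assessment of major body systems: abdominal, respiratory, cardiovascular, general appearance, head, eyes, ears/nose/throat, lymph nodes", followed by musculoskeletal, neck, neurological, dermatological and a residual category. For the shorter one: "The abbreviated physical examination will consist of a routine assessment of the following body systems: abdominal, respiratory, cardiovascular, general appearance", again with a residual category.

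Protocol Table 9-1, footnote c (printed under Section 9.1.2) assigns them to visits: "Complete physical examination will be performed at Visit 1 and an abbreviated physical examination will be performed at all other specified time points". Footnote c of SAP Table 1 has the same rule.

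Protocol 14.3.3 plans the reporting: "Physical examination data will be summarized descriptively (number and percentage of the subjects) in tables by treatment and time point". It excludes no body system.

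SAP 8.3.5 says: "Physical examination will be summarized with the number and percentage of the subjects for clinically relevant categories", the categories being normal, abnormal not clinically significant and abnormal clinically significant. It then lists 12 body systems. The list goes from abdominal directly to cardiovascular. It names no visits and no denominator.

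The general rule in SAP 6.1 therefore applies: "The denominator for the percentages will be the total number of subjects in the treatment group and analysis population being presented", unless something else is specified. SAP 6.1 also makes analysis visit by treatment group the default layout.

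SAP section 1 gives the SAP precedence over the protocol's statistical text. SAP section 10 reports no changes from the protocol.

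**The concern.** Few categories are routinely examined once subjects are on treatment, and respiratory is one of them. Because the SAP takes precedence, a programmer working from 8.3.5 would build a table without it, and nothing in the SAP marks the omission as intended. The listings would keep the data but give no side-by-side comparison of arms. That matters most for findings graded abnormal but not clinically significant. SAP 8.3.5 tabulates that grade for every other system, and such findings need not become adverse events.

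A second, smaller gap concerns layout. Most of the listed systems belong only to the Visit 1 examination, but SAP 8.3.5 does not say which rows apply at which visits. The reporting grid in SAP 9.3 does not help: its safety part has columns for laboratory tests, vital signs, ECG and nevi, but none for physical examination. The default denominator counts subjects who were not examined for the system in question.

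**Working it through.** The plan states no figure to reproduce. The check compares three lists.

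**Inputs**

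| Category | Complete (Protocol 10.9.1; Visit 1) | Abbreviated (Protocol 10.9.1; other visits) | SAP 8.3.5 list |
|---|---|---|---|
| Abdominal | yes | yes | yes |
| Respiratory | yes | yes | **no** |
| Cardiovascular | yes | yes | yes |
| General appearance | yes | yes | yes |
| Head | yes | no | yes |
| Eyes | yes | no | yes |
| Ears/nose/throat | yes | no | yes |
| Lymph nodes | yes | no | yes |
| Musculoskeletal | yes | no | yes |
| Neck | yes | no | yes |
| Neurological | yes | no | yes |
| Dermatological | yes | no | yes |
| Other | yes | yes | yes |
| **Total** | **13** | **5** | **12** |

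**Comparison**

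- Complete but not in SAP: 13 − 12 = 1, respiratory.
- In SAP but not in the complete examination: none. Apart from respiratory, the SAP list is the protocol's complete list.
- Abbreviated but not in SAP: respiratory. So 5 − 1 = 4 categories examined after Visit 1 have a row.
- In SAP but not in the abbreviated examination: 12 − 4 = 8, from head to dermatological in the table.

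**Is the gap an artefact of the text?** The missing item falls mid-list, between abdominal and cardiovascular. The list's one visible break comes later, after ears/nose/throat. Nothing at the gap suggests a redaction or lost text.

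**Denominator.** Under SAP 6.1 the printed percentage is (number with the finding) / (all subjects in the group). Among those examined it is (number with the finding) / (number examined). The first equals the second multiplied by (number examined / group size). As an illustration only, suppose the share without a Week 26 examination equals the 20% dropout assumed in Protocol 14.2. The factor is then 1 − 0.20 = 0.80, and each whole-group percentage is four fifths of the percentage among those examined. For the eight Visit 1 systems, the number routinely examined at later visits is zero by design, so a percentage there carries no information.

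**After the change.** Adding respiratory gives 12 + 1 = 13 categories, identical to Protocol 10.9.1. All 5 abbreviated-examination categories would be tabulated at later visits.

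**The case against.** The strongest reply is that one descriptive row is missing and little is lost. Much of that stands.

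- Respiratory findings do not vanish. Under Protocol 12.1 and 12.6, abnormal findings that meet the criteria are recorded as adverse events, and SAP 8.3.1 tabulates those. SAP 8.3.3 summarises respiratory rate with a shift table. SAP 8.3 lists all safety data. What goes unsummarised is respiratory examination findings not reported as adverse events.
- SAP 6.1 allows percentages to be based on subjects with available data. It does so as an exception to be specified, and SAP 8.3.5 does not specify it.

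A reader might also infer three stronger things that the documents do not support.

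- *That listing the eight systems is an error.* They are examined at Visit 1. The protocol plans the table by time point, and SAP Table 4 has Screening as an analysis visit. A table covering Visit 1 needs those rows.
- *That later rows for these systems would pass as examined and normal.* SAP 8.3.5 also tabulates Normal. With nobody examined, Normal and Abnormal are both zero, which looks like missing data. No table shell shows that such rows would be printed, and SAP 9.1 leaves zero percentages blank.
- *That skin and nervous system go unobserved after screening, hiding a known signal.* Protocol 10.9.4 requires a full-body visual nevi examination, scheduled after baseline as well, and the abbreviated examination keeps its residual category. The Phase 2 skin and nervous-system findings in Protocol 5.2 and 7.4 were adverse events, which the adverse-event tables would capture.

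None of this explains why respiratory is absent from the list.

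**Conclusion.** The omission is an error in SAP 8.3.5 as written: one category, examined at every examination visit, has no row in the summary of a listed safety endpoint, and the SAP does not declare the departure. The table would be incomplete; nothing here shows that any tabulated count would be wrong, so it would be too strong to say that the endpoint is misreported.

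The visit and denominator gap is real but secondary. The eight systems are validly listed, and what is missing is a rule for where they appear and over whom percentages are taken.

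Severity is minor. Physical examination is summarised descriptively and lies outside the H1 to H12 testing sequence, so efficacy, power and type I error are untouched. The conclusion assumes that the output follows the SAP text; a table shell, which the documents do not show, might already include respiratory.

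**What to change.** In SAP 8.3.5:

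1. Add Respiratory between Abdominal and Cardiovascular, so that the list matches Protocol 10.9.1.
2. State that head, eyes, ears/nose/throat, lymph nodes, musculoskeletal, neck, neurological and dermatological are tabulated at Visit 1 only, and that abdominal, respiratory, cardiovascular, general appearance and other are also tabulated at later examination visits.
3. State that percentages use the subjects examined for that system at that visit, as a specified exception to SAP 6.1.

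For consistency, add a physical-examination column to the safety grid in SAP 9.3.

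The cost is SAP wording and a table-shell edit. No new data, visits or procedures are needed. The only visible consequence is a shorter table after Visit 1.
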